# 3. ENDPOINTS AND BASELINE VARIABLES: DEFINITIONS AND CONVENTIONS

# 3.1. Primary Endpoints

## Cohort 1

• Skin irritation index.

## Cohort 2

• Adverse events (AEs), clinical laboratory tests, vital signs, and 12 lead electrocardiogram (ECG).

## 3.2. Secondary Endpoints

#### Cohort 1

• AEs.

# Cohort 2

• PK parameters:  $C_{max}$ ,  $T_{max}$ ,  $AUC_{last}$ ,  $AUC_{24}$ ,  $AUC_{\tau}$  on Day 1 and Day 8, and  $R_{ac}$  ( $C_{max}$ ) and  $R_{ac}$  ( $AUC_{\tau}$ ) on Day 8.

## 3.3. Other Endpoints

## 3.3.1. PK Endpoints

PK parameters are the secondary endpoints for Cohort 2. For each subject, the following PK parameters will be calculated for crisaborole and its identified main oxidative metabolites (AN7602 and AN8323), as data allows using noncompartmental analysis of concentration-time data.

Parameter	Day	Definition	Method of Determination
$AUC_{\tau}$	1, 8	Area under the plasma concentration-time curve from time zero to time tau $(\tau)$ , the dosing interval, where $\tau = 12$ hours for BID dosing	Linear/Log trapezoidal method
AUC last	1, 8	Area under the plasma concentration-time curve from zero time until the last measurable concentration ( $C_{last}$ )	Linear/Log trapezoidal method
$AUC_{24}$	1, 8	Area under the plasma concentration-time curve from time zero to the 24 hours postdose	Linear/Log trapezoidal method
$C_{\text{max}}$	1, 8	Maximum observed plasma concentration over the dosing interval (12 hours) and over a 24 hour time period (total daily dose)	Observed directly from data
$T_{\text{max}}$	1, 8	Time to reach maximum observed plasma concentration	Observed directly from data as time of first occurrence
$R_{ac}(C_{max})$	8	Accumulation ratio for C max	C max, Day 8 /C max(first dose)
$R_{ac} (AUC_{\tau})$	8	Accumulation ratio for $AUC_{\tau}$	$AUC_{\tau, Day 8}/AUC_{\tau(first dose)}$

#### 3.4. Baseline Variables

There are no baseline variables used as covariates or stratification factors in analyses.

# 3.5. Safety Endpoints

#### 3.5.1. Adverse Events

AEs will be captured and reported in accordance with Pfizer data standards.

An adverse event is considered treatment emergent relative to a given treatment if:

- the event occurs for the first time during the effective duration of treatment and was not seen prior to the start of treatment (for example, during the baseline or run-in period), or
- the event was seen prior to the start of treatment but increased in severity during treatment.

The effective duration of treatment is determined by the lag time. Any event occurring within the lag time, whether this occurs during a break in treatment or at the end of treatment, is attributed to the corresponding treatment period. An infinite lag will be used for this study.

#### 4. ANALYSIS SETS

Data for all subjects will be assessed to determine if subjects meet the criteria for inclusion in each analysis population prior to unblinding and releasing the database and classifications will be documented per standard operating procedures.

#### 4.1. Full Analysis Set

Not Applicable.

#### 4.2. Per Protocol Analysis Set

Not Applicable.

## 4.3. Safety Analysis Set

The safety analysis population is defined as all subjects who receive at least one dose of study medication. All subjects who receive at least one dose of study medication are classified according actual study treatment received. The safety analysis set is the primary population for treatment administration/compliance and safety. A randomized but not treated

subject will be excluded from the safety analyses. A treated but not randomized subject will be reported under the treatment actually received.

## 4.4. Other Analysis Sets

## 4.4.1. PK Analysis Sets

- The PK concentration population is defined as all subjects randomized and treated who have at least 1 concentration.
- The PK parameter analysis population is defined as all subjects randomized and treated who have at least 1 of the PK parameters of primary interest.

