## 5.3.3. Concentrations Below the Limit of Quantification (BLQ)

In all data presentations (except listings), concentrations BLQ will be set to zero (In listings BLQ values will be reported as "<LLQ", where LLQ will be replaced with value for the lower limit of qualntification).

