# 5.3.4. Deviations, Missing Concentrations and Anomalous Values for PK

In summary tables and plots of mean and median profiles, statistics will be calculated having set concentrations to missing if one of the following cases is true:

- A concentration has been collected as ND (ie, not done) or NS (ie, no sample);
- A deviation in sampling time is of sufficient concern (ie, sampling time outside of 20% of nominal time) or a concentration has been flagged anomalous by the pharmacokineticist.

Note that summary statistics will not be presented at a particular time point if more than 50% of the data are missing.

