#### 5.3.5. Pharmacokinetic Parameters

Actual PK sampling times will be used in the derivation of PK parameters.

If a PK parameter cannot be derived from a subject's concentration data, the parameter will be coded as NC (ie, not calculated). (Note that NC values will not be generated beyond the day that a subject discontinues).

In summary tables, statistics will be calculated by setting NC values to missing; and statistics will not be presented for a particular treatment if more than 50% of the data are NC.

If an individual subject has a known biased estimate of a PK parameter (for example, due to an unexpected event before all the drug is absorbed in the body), this will be footnoted in summary tables and will not be included in the calculation of summary statistics or statistical analyses.

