#### 6.1.2. Adverse Events

AEs are one of the primary endpoints for Cohort 2. The analysis of AEs will be based on the safety analysis population. Descriptive summaries and listing of the AE/SAE data will be provided by treatment. In addition, AEs occurred in the treatment area will be separately summarized by treatment. AEs will be reported in accordance with the Pfizer data standards.

It should be recognized that most studies are not designed to reliably demonstrate a causal relationship between the use of a pharmaceutical product and an adverse event or a group of adverse events. Except for select events in unique situations, studies do not employ formal adjudication procedures for the purpose of event classification. As such, safety analysis is generally considered as an exploratory analysis and its purpose is to generate hypotheses for further investigation.

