#### 6.2.2. PK Parameters

PK parameters are the secondary endpoints for Cohort 2. PK analysis will be based on the PK analysis set.

PK data will be descriptively summarized by day and analyte for crisaborole and its metabolites respectively. Comparison between days will be performed by descriptive analysis of the within-subject ratio of Day 8/Day 1 PK parameters. The set of summary statistics as specified in the table below:

Day	Parameter	Summary statistics	
1, 8	$AUC_{\tau}$ , $AUC_{last}$ , $AUC_{24}$ , $C_{max}$	n, arithmetic mean, median, CV%, standard deviation,	
		minimum, maximum, geometric mean, geometric CV%	
1, 8	T max	n, median, minimum, maximum	
8	$R_{ac}$ ( $C_{max}$ ), $R_{ac}$ ( $AUC_{\tau}$ )	n, arithmetic mean, median, CV%, standard deviation,	
		minimum, maximum, geometric mean, geometric CV%	

A summary of concentrations by day and nominal time point, for crisaborole and its metabolites respectively, where the set of statistics will include n, mean, median, standard deviation, CV(%), minimum, maximum and the number of concentrations above the lower limit of quantification.

Mean and median profiles of the plasma concentration-time data will be plotted through Day 1 to Day 9, for crisaborole and its metabolites respectively. In addition, mean and median profile of trough concentration data on Day 7, Day 8 and Day 9 will be plotted against time for crisaborole and its metabolites respectively. Mean and median profiles against nominal time point will be presented on both linear and semi-log linear scales.

Individual plasma concentration-time data will be plotted through Day 1 to Day 9, for crisaborole and its metabolites respectively. In addition, the individual plasma concentration-time data for all subjects will be plotted through Day 1 to Day 9 on the same graph, for crisaborole and its metabolites respectively. Individual profiles against actual time point will be presented on both linear and semi-log linear scales.

All plasma concentration values and plasma PK parameters will be listed by subject.

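### Could the two vehicle subjects in Cohort 2 be pooled into the crisaborole PK summaries as zeros?

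*SAP*

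**What the plan says.** Cohort 2 randomizes about 12 subjects 5:1, ten to crisaborole ointment 2% and two to vehicle (Protocol 5.1 and 9.1). The vehicle contains no active drug (Protocol 5). PK samples are scheduled for the cohort without distinction by arm, and no arm is exempted from assay (Schedule of Activities; Protocol 6.2.2 and 7.2.1).

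The concentration set in SAP 4.4.1 reads: "The PK concentration population is defined as all subjects randomized and treated who have at least 1 concentration". The parameter set is built the same way, and Protocol 9.3 repeats both.

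On layout, SAP 6.2.2 says: "PK data will be descriptively summarized by day and analyte for crisaborole and its metabolites respectively". It tabulates concentrations by day and nominal time point. On BLQ values, SAP 5.3.3 says: "In all data presentations (except listings), concentrations BLQ will be set to zero". Protocol 9.3 applies the same zero rule when parameters are derived.

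There are two suppression rules. For concentrations (SAP 5.3.4): "summary statistics will not be presented at a particular time point if more than 50% of the data are missing". For parameters (SAP 5.3.5): "statistics will not be presented for a particular treatment if more than 50% of the data are NC".

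The PK objective (Protocol 2, SAP 2.1) is to characterize plasma PK after repeated crisaborole dosing.

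**The concern.** The PK section is the exception in a SAP that otherwise splits Cohort 2 by arm. For adverse events, for instance, SAP 6.1.2 says: "Descriptive summaries and listing of the AE/SAE data will be provided by treatment". Laboratory, vital sign, ECG, baseline and exposure summaries are split the same way. A programmer who took SAP 4.4.1, 5.3.3 and 6.2.2 at face value could produce one PK table with n = 12, two of the twelve contributing zeros.

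That would understate exposure in a cohort meant to show the possible maximum systemic exposure in Japanese patients under maximal use (Protocol 1.4.1), and understatement is the less cautious direction. The SAP also does not say how each parameter from an all-BLQ profile is coded. Cmax could be read as zero, whereas AUClast is defined as "Area under the plasma concentration-time curve from zero time until the last measurable concentration" and has no end point if nothing was measurable. One table could then mix n = 10 and n = 12.

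**Working it through.** **Inputs.** Arm sizes 10 and 2 (Protocol 9.1), which the ratio reproduces: 12 × 5/6 = 10 and 12 × 1/6 = 2. The documents give no variability for Japanese adults, so the coefficients of variation (CVs) below are assumptions. The upper one, 196/127 = 1.54, is the Day 8 crisaborole Cmax SD over mean in Protocol Table 1, from subjects aged 2–17, and is used only as a bound.

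**Worst case: vehicle samples assayed, all BLQ, set to zero and pooled.**

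- *Mean.* Pooled mean = 10m/12 = 0.833m, a fall of 16.7% whatever the variability. With the Table 1 mean of 127 ng/mL for illustration, 127 × 10/12 = 105.8 ng/mL.
- *CV.* For ten values with mean 1 and SD c plus two zeros, pooled CV = √[(9c² + 10 − 12 × (10/12)²)/11] ÷ (10/12).
- *Median.* The middle pair of twelve values is the 4th and 5th ordered crisaborole values instead of the 5th and 6th. The ratio below is the typical within-sample ratio over 400,000 simulated log-normal samples of ten.

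| Assumed CV | Pooled CV | n = 12 median ÷ n = 10 median |
|---|---|---|
| 0.50 | 0.72 | 0.90 |
| 1.00 | 1.18 | 0.83 |
| 1.54 | 1.74 | 0.79 |

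- *Minimum and geometric statistics.* The minimum becomes 0. For any parameter coded zero, the geometric mean is 0 or undefined and the geometric CV cannot be computed.
- *Unaffected.* Maxima do not move. Accumulation and Day 8/Day 1 ratios are 0/0 for a vehicle subject, hence NC and treated as missing. AUClast and Tmax are probably NC too.

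**Do the suppression rules prevent this?** Not in a pooled table: 2/12 = 16.7% is below 50%, and a BLQ value set to zero is not missing.

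**Does the plan ask for pooling?** Four places bear on it.

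1. The objective is PK after crisaborole doses. Vehicle subjects receive none and cannot contribute to that quantity.
2. The SAP 5.3.5 rule withholds statistics for a treatment, which presupposes that parameter summaries belong to one. In a by-treatment table with vehicle parameters coded NC, 2/2 = 100% exceeds 50% and the vehicle column is left blank, a sensible result.
3. SAP 6.2.2 requires the geometric mean and geometric CV of Cmax and the AUCs. Pooling zeros defeats those statistics; separating the arms does not.
4. SAP 4 requires analysis sets to be settled "prior to unblinding and releasing the database". A set definition that ignores arm is what a blinded classification needs. It says who has usable PK data, and does not say that arms are merged in the tables.

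With PK shown by treatment or for crisaborole subjects only, n = 10 and the effect is zero.

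**The case for a change.** The best case for a change is that it is cheap: one clause in SAP 6.2.2 would remove all doubt, and SAP version 2.0 clarified other sections after a blind table review but left this one. The SAP 5.3.5 wording governs parameters only and does not fix the table layout; the matching concentration rule in SAP 5.3.4 is per time point. For the concentration tables and the mean and median profiles, then, no sentence names treatment.

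That reading of the text is correct, and so is the arithmetic. What does not follow is that pooling is the likely outcome. Silence on treatment is not an instruction to merge arms, and a per-time-point rule works equally well inside a by-treatment table. The secondary endpoint is the set of PK parameters, which is where the treatment wording does appear. The concentration summaries support that endpoint and would naturally follow the same split.

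Nor could the error stay hidden. An n of 12, minima of zero at post-dose times, failed geometric means and the count of values above the quantification limit would each reveal it. SAP 6.2.2 already lists every concentration by subject, so vehicle values, if assayed, can be checked for contamination or mis-dosing without new text. Coding of all-BLQ profiles hardly matters once the crisaborole summaries stand alone.

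**Conclusion.** The omission is real, but it is a gap that an analyst fills correctly from the objective, SAP 5.3.5 and the planned statistics. The 16.7% fall in means is a conditional worst case, not an expected bias. It needs vehicle samples to be assayed, BLQ and pooled, and for Cmax, AUCtau and AUC24 also coded as zero rather than NC. That vehicle samples are assayed and BLQ is inferred, not stated; the median and CV figures rest on assumed log-normal variability. The table layouts are not in the documents, so whether PK is shown by treatment cannot be confirmed from them.

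SAP 5.1 tests no hypothesis and sets no decision rule, so no inference turns on the point. The arm-neutral set definitions in SAP 4.4.1 suit a blinded classification and should stay. No change to the plan is needed.

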#### 4.5. Protocol Deviations

Subjects who experience events that may affect their PK profile may be excluded from the PK analysis. At the discretion of the pharmacokineticist a concentration value may also be excluded if the deviation in sampling time is of sufficient concern or if the concentration is anomalous for any other reason.

A full list of protocol deviations will be complied and reviewed to identify major and minor deviation prior to database closure.

#### 5. GENERAL METHODOLOGY AND CONVENTIONS

- The final analysis will be performed at study subjects' dataset release after last subject last visit.
- All data will be analyzed separately for each cohort.

## 5.1. Hypotheses and Decision Rules

There are no statistical hypotheses to be tested.

#### **5.2. General Methods**

## 5.2.1. Analyses for Binary Data

Unless otherwise explicitly stated, descriptive statistics for binary variables are the percentage (%), and the numerator (n) and the denominator (N) used in the percentage calculation

#### 5.2.2. Analyses for Continuous Data

Unless otherwise explicitly stated, descriptive statistics for continuous variables are n, mean, median, standard deviation, minimum, and maximum.

#### 5.3. Methods to Manage Missing Data

## 5.3.1. Safety Data

Handling of missing information related to safety data, such as missing or partially missing data, will be in accordance with Pfizer data standards.

#### 5.3.2. Skin Irritation Score

Missing values of the skin irritation score will not be imputed in any data analysis.

## 5.3.3. Concentrations Below the Limit of Quantification (BLQ)

In all data presentations (except listings), concentrations BLQ will be set to zero (In listings BLQ values will be reported as "<LLQ", where LLQ will be replaced with value for the lower limit of qualntification).

# 5.3.4. Deviations, Missing Concentrations and Anomalous Values for PK

In summary tables and plots of mean and median profiles, statistics will be calculated having set concentrations to missing if one of the following cases is true:

- A concentration has been collected as ND (ie, not done) or NS (ie, no sample);
- A deviation in sampling time is of sufficient concern (ie, sampling time outside of 20% of nominal time) or a concentration has been flagged anomalous by the pharmacokineticist.

Note that summary statistics will not be presented at a particular time point if more than 50% of the data are missing.

#### 5.3.5. Pharmacokinetic Parameters

Actual PK sampling times will be used in the derivation of PK parameters.

If a PK parameter cannot be derived from a subject's concentration data, the parameter will be coded as NC (ie, not calculated). (Note that NC values will not be generated beyond the day that a subject discontinues).

In summary tables, statistics will be calculated by setting NC values to missing; and statistics will not be presented for a particular treatment if more than 50% of the data are NC.

If an individual subject has a known biased estimate of a PK parameter (for example, due to an unexpected event before all the drug is absorbed in the body), this will be footnoted in summary tables and will not be included in the calculation of summary statistics or statistical analyses.

#### 6. ANALYSES AND SUMMARIES

## 6.1. Primary Endpoints

#### 6.1.1. Skin Irritation Index

Skin irritation index is the primary endpoint for Cohort1. For each investigational product (ie, treatment), the skin irritation index will be calculated as the sum of the individual maximum irritation scores divided by the number of evaluable subjects who have the skin irritation assessment for the safety analysis population and multiplied by 100. The calculated skin irritation index will range from 0 to 400. As show in the following table, for example, when the skin irritation index is equal to or smaller than 5, the investigational product will be categorized as 'Safe'. 1,2,3

## **Safety Criteria of Skin Irritation Index**

Skin irritation index a	Category
0≤ - ≤5	Safe
5< - ≤15	Acceptable
15< - ≤30	Improvable
30< - ≤400	Risky

a: Skin irritation index = (Sum of individual maximum irritation scores / number of evaluable subjects)  $\times$  100

#### 6.1.2. Adverse Events

AEs are one of the primary endpoints for Cohort 2. The analysis of AEs will be based on the safety analysis population. Descriptive summaries and listing of the AE/SAE data will be provided by treatment. In addition, AEs occurred in the treatment area will be separately summarized by treatment. AEs will be reported in accordance with the Pfizer data standards.

It should be recognized that most studies are not designed to reliably demonstrate a causal relationship between the use of a pharmaceutical product and an adverse event or a group of adverse events. Except for select events in unique situations, studies do not employ formal adjudication procedures for the purpose of event classification. As such, safety analysis is generally considered as an exploratory analysis and its purpose is to generate hypotheses for further investigation.

#### 6.1.3. Laboratory Data

Laboratory data are one of the primary endpoints for Cohort 2. The analysis of laboratory data will be based on the safety analysis population. Laboratory data will be descriptively summarized and listed by treatment in accordance with the Pfizer data standards. Baseline will be the last predose measurement.

#### 6.1.4. Vital Signs

Vital signs data are one of the primary endpoints for Cohort 2. The analysis of vital signs data will be based on the safety analysis population. Absolute values and changes from

baseline in blood pressure and pulse rate will be summarized and listed by treatment and visit in accordance with the Pfizer data standards. Baseline will be the last predose measurement.

## 6.1.5. Electrocardiogram

ECG data are one of the primary endpoints for Cohort 2. Absolute values and changes from baseline for the ECG parameters, QT interval, heart rate, QTc (ie, QTcF) interval, PR interval, QRS interval, and RR interval will be summarized descriptively by treatment and visit for the safety analysis population.

The number (%) of subjects with maximum postdose QTc values and maximum increases from baseline in the following categories will be tabulated by treatment:

## **Safety QTc Assessment**

	Borderline (msec)	Prolonged (msec)
Absolute value	≥450 - <480	≥480
Absolute change	30 - <60	≥60

In addition, the number of subjects with corrected and uncorrected QT values ≥500 msec will be summarized.

#### 6.2. Secondary Endpoints

#### **6.2.1.** Adverse Events

AEs are the sencondary endpoint for Cohort 1. The analysis of AEs will be based on the safety analysis population. Descriptive summaries and listing of the AE/SAE data will be provided. In addition, AEs occurred in the application area will be summarized by treatment separately. AEs will be reported in accordance with the Pfizer data standards.

#### 6.2.2. PK Parameters

PK parameters are the secondary endpoints for Cohort 2. PK analysis will be based on the PK analysis set.

PK data will be descriptively summarized by day and analyte for crisaborole and its metabolites respectively. Comparison between days will be performed by descriptive analysis of the within-subject ratio of Day 8/Day 1 PK parameters. The set of summary statistics as specified in the table below:

Day	Parameter	Summary statistics	
1, 8	$AUC_{\tau}$ , $AUC_{last}$ , $AUC_{24}$ , $C_{max}$	n, arithmetic mean, median, CV%, standard deviation,	
		minimum, maximum, geometric mean, geometric CV%	
1, 8	T max	n, median, minimum, maximum	
8	$R_{ac}$ ( $C_{max}$ ), $R_{ac}$ ( $AUC_{\tau}$ )	n, arithmetic mean, median, CV%, standard deviation,	
		minimum, maximum, geometric mean, geometric CV%	

A summary of concentrations by day and nominal time point, for crisaborole and its metabolites respectively, where the set of statistics will include n, mean, median, standard deviation, CV(%), minimum, maximum and the number of concentrations above the lower limit of quantification.

Mean and median profiles of the plasma concentration-time data will be plotted through Day 1 to Day 9, for crisaborole and its metabolites respectively. In addition, mean and median profile of trough concentration data on Day 7, Day 8 and Day 9 will be plotted against time for crisaborole and its metabolites respectively. Mean and median profiles against nominal time point will be presented on both linear and semi-log linear scales.

Individual plasma concentration-time data will be plotted through Day 1 to Day 9, for crisaborole and its metabolites respectively. In addition, the individual plasma concentration-time data for all subjects will be plotted through Day 1 to Day 9 on the same graph, for crisaborole and its metabolites respectively. Individual profiles against actual time point will be presented on both linear and semi-log linear scales.

All plasma concentration values and plasma PK parameters will be listed by subject.

